3.4 Measures

3.4.1 Semi-structured assessment interview

This audio-recorded 60-minute interview will follow the format of an initial psychological assessment and will allow discussion of presenting problems and relevant personal and social history. This will allow potential predisposing and precipitating factors to be identified. Participants' experiences of IDAs will also be discussed, focussing on thoughts, feelings and behaviour before and after the episodes. The participants will also be asked about the impact that these have had on their everyday functioning.

3.4.2 IDA record

Participants will be asked to write an account of any IDAs. They will be shown an example diary and will also be given a prompt sheet, asking them to recall any triggers, feelings, physical arousal, thoughts and behaviour both directly before and after the episode. This diary will be completed by participants as close to the episode as possible.

4 Sample size

In order to address all three of the research questions, a qualitative approach will be used. An overall sample size of ten should be sufficient to allow themes to be identified. A purposive sampling method will be used to recruit younger participants as well as those who are in the average age range for onset. This will allow any differences between these two groups to be explored further. As the inclusion criteria specifies 6+ IDAs per year, this will ensure a fairly homogenous sample in terms of frequency of IDAs.

There is a sample of approximately 40 patients who had ongoing drop attacks in July 2016 which can be recruited from. One to two new referrals per month are currently being made to

[name], and these patients can also be approached. This is a relatively small pool and there can be some unwillingness to engage with a psychological approach within the functional neurological population. However, as this study is aiming to help better understand participants' experiences, rather than investigating psychological treatment, this may enhance engagement. Attrition is also a factor but, as the primary research question relies on information from the initial interview, the risk of this is reduced. Therefore, recruiting a purposive sample of ten participants should be achievable.

5 Analysis

The content of the psychological interviews and diaries will be analysed using a grounded theory approach in order to meet all of the study objectives. Using both initial interviews and recorded accounts will allow information to be obtained from different viewpoints, enriching the data. This data will be coded by initially naming each segment of data and then synthesising the most common codes to identify themes. From these, theories can be developed regarding predisposing and precipitating factors. Themes regarding thoughts, emotions and behaviour can also be explored.

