Developing a psychological understanding of idiopathic drop attacks

Study Protocol

Version 3

[name]

15th January 2018

1 Introduction

Idiopathic drop attacks (IDAs) have been defined as falls to the floor without warning, where there is no identified organic cause, despite diagnostic testing. They are not caused by malfunction of the lower limbs, changes in body or head posture, or vertigo. There is also no loss of consciousness and recovery is rapid. Despite this fast recovery, people can experience significant injuries and fear about further falls, impacting on their everyday functioning.

This phenomenon was highlighted by Stevens and Matthews (1973) who recruited 33 patients from a neurology clinic and seven from a gynaecological clinic. They also approached 100 men who were admitted for routine surgery but found that none of these had experienced drop attacks. Therefore their sample was entirely female, with onset occurring on average at age 44. Although the age-range of onset spanned from 19 to 69, in two thirds of the sample onset was between the ages of 40 and 59.

The authors ruled out obesity, vascular disease, epilepsy, vestibular disease, limb weakness and hypothyroidism as contributing to IDAs. They investigated hormonal changes, given that the age of onset coincided with when menopause could be likely to start and due to the fact that 60% of the younger patients had onset of IDAs during pregnancy. Despite this, the authors found no clear links between hormonal changes and IDAs, although 45% did experience onset either during pregnancy or within 3 years either side of the start of the menopause.

The frequency of IDAs varied greatly between individuals but ranged from two to more than 12 falls per year, usually while walking. This was more likely to happen when out of the house but over half of the sample also reported falling at home. These falls would lead to injury to the knees and often also to the hands, chest and face. 18% reported having fractured or broken bones as a result of an IDA. Given the age of onset, the increased likelihood of osteoporosis would also increase the risk of more severe injury as a result of IDAs. The authors also reported that many women would become afraid to go out due to both the risk of injury and embarrassment.

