Although it is undocumented, the prevalence of IDAs could be relatively high. As part of their recruitment process, the Stevens and Matthews (1973) asked 200 consecutive patients at a gynaecology clinic whether they had experienced falls and found that 3.5% met the criteria for IDA. This suggests that this phenomenon could account for a significant number of falls in women in the general population.

There are similarities between IDAs and psychogenic non-epileptic seizures (PNES). However, IDAs are not included widely included in studies of PNES, which tend to focus on 'convulsive' seizures. Hubsch et al. (2011) analysed clinical signs in 145 PNES and identified different subtypes of seizure, none of which covered IDAs. However, Galimberti et al (2003) and Devinsky et al (1996) included patients with IDA within a PNES sample, accounting for around 10% of each sample. There has been no published research investigating this group in isolation since Stevens and Matthew's (1973) study other than a small number of case reports (Butsch & Schneemann, 2014), one of which identified a woman's IDAs as occurring following recollection of traumatic experiences, suggesting a psychological mechanism (Wilner et al., 2010).

A paper which is currently being prepared for submission by [name], [name] & [name] at the Department of Clinical Neurosciences, Edinburgh, identified 83 patients who had attended a neurology clinic over nine years who described experiencing these attacks. This led the authors to develop a hypothesis that IDAs are a conditioned behavioural response to negative external (environmental or situational) or internal (anxiety symptoms or dissociation) stimuli. This association is maintained through fear of collapse and/or through the fall providing relief from the negative stimuli. This type of mechanism has been highlighted previously in functional neurological disorders, where limbic regions were found to have a greater influence on motor preparatory regions when in a state of arousal (Voonet al., 2011).

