As the underlying mechanism of IDAs is unknown, there is currently no treatment available. However, Hoeritzauer and colleagues report that a small number of patients saw their IDAs resolve following an explanation of the episodes as conditioned responses and the use of distraction techniques. A psychological understanding of the problem could help to identify a potential psychological intervention. Such interventions have been found to be effective for PNES, particularly cognitive behavioural therapy (Goldstein et al., 2010). This type of intervention could focus on helping individuals to manage their condition and improve the ways they cope with the anxiety surrounding future falls, rather than necessarily seek to resolve the IDAs.

This research aims to explore a psychological understanding of drop attacks. This will be investigated through the collection of qualitative data from interviews and recorded diaries from individuals experiencing IDAs. The data will be analysed using a grounded theory approach in order to better understand the onset of drop attacks, the impact of life stressors as well as thoughts, feelings and behaviour both directly before and after a IDA.

2 Aims

The main aim of this research is to develop a psychological understanding of idiopathic drop attacks. The primary research question is as follows:

- What are the predisposing and precipitating factors related to the onset of IDAs?

Secondary research questions are:

- What are individuals' thoughts, emotions and behaviour immediately prior to an IDA?
- What are individuals' thoughts, emotions and behaviour immediately following an IDA?

3 Methods

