3.1 Participants

Participants will be ten individuals who are experiencing ongoing IDAs. Inclusion criteria are 1) Aged 18+, 2) IDAs occurring 6+ times per year, 3) Able to provide informed consent.

Exclusion criteria are 1) Diagnosis which would provide an alternative explanation for drop attacks.

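### Must Section 4 say whether its two purposive age groups mean present age or age at onset?

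*Protocol*

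**What the plan says.** Section 4 (Sample size) sets the selection rule, "A purposive sampling method will be used to recruit younger participants as well as those who are in the average age range for onset", and gives its purpose: "This will allow any differences between these two groups to be explored further". It states no age variable, cut-off or number per group.

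The surrounding text gives the context:

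- Section 2 (Aims) puts the primary question as "What are the predisposing and precipitating factors related to the onset of IDAs".
- Section 3.1 says "Participants will be ten individuals who are experiencing ongoing IDAs". It requires age 18 or over and at least six attacks a year, and sets no condition on age at onset or time since onset.
- Section 1 describes the 1973 series as "with onset occurring on average at age 44" and adds that "in two thirds of the sample onset was between the ages of 40 and 59". The range of onset was 19 to 69.
- Section 4 describes the recruitment pool as "approximately 40 patients who had ongoing drop attacks in July 2016", with one to two new referrals a month. Section 6 starts both recruitment and data collection in January 2018 and ends data collection in December 2018.

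**The concern.** The selection rule describes one group by how old the participants are and the other by a range of onset ages. Taken at face value it could mean present age for both. In a sample of people who already have the condition, present age is never below age at onset, so any discrepancy runs one way. A group chosen as now being 40 to 59 can include people whose attacks began earlier, and people with mid-life onset who are now 60 or older might not be sought. The younger group cannot be affected in the same way, since nobody now under 40 can have had onset at 40 or later.

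The primary question is about what brings attacks on, so a blurred onset grouping would blur which accounts stand for typical onset. Selection also happens at recruitment, and with ten participants there is little room to rebalance afterwards.

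**Working it through.** **Is the grouping variable defined anywhere?** No. Sections 3.1, 3.3, 4 and 5 do not define it. The sample size of ten rests on a qualitative judgement, so there is no formula to reproduce, and neither reading changes it.

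**Which reading does the text favour?** Neither is excluded. The only yardstick in the sentence is a range for onset, and Section 1 discusses age almost entirely as age at onset. Section 1 also speaks of younger patients in an onset context, when it reports that 60% of them had their first attacks during pregnancy. Against that background, younger-onset against typical-onset is a natural meaning.

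**When does a person end up in the wrong group?** Take onset at 25 and present age 45, with 40 to 59 assumed as the typical range.

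- Groups defined by present age: the person belongs in the 40 to 59 group and is correctly placed.
- Groups defined by age at onset: the person belongs in the younger group and is correctly placed.
- Selected on present age, then interpreted by onset: misplaced. No section says this will be done.

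**How many could be affected in that third case?** The one interval the documents support is July 2016 to January 2018, which is 18 months. It is a minimum for the existing pool; new referrals may be more recent. The rest is assumed: the 40 to 59 band, the same time since onset D for everyone, five places in the group, and an onset distribution matched to the 1973 series.

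Share of those now 40 to 59 with onset before 40 = P(40 − D ≤ onset < 40) / P(40 − D ≤ onset < 60 − D).

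- *Model (a)*: uniform within three bands, with weight 0.310 on 19 to 39 (21 years), 0.667 on 40 to 59 (20 years) and 0.023 on 60 to 69. The mean is 0.310 × 29.5 + 0.667 × 50 + 0.023 × 65 = 44.0.
- *Model (b)*: normal, mean 44, SD 8, truncated to 19 to 69. Band weights are 0.308, 0.670 and 0.022.

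At D = 1.5 years:

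- (a): (1.5/21 × 0.310) / (1.5/21 × 0.310 + 18.5/20 × 0.667) = 0.0221 / 0.6391 = 3.5%.
- (b): 8.7%.
- Of five people: 5 × 0.035 = 0.2 to 5 × 0.087 = 0.4.

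The share grows with D: 12.9% (a) to 22.7% (b) at 5 years, and 30.7% to 36.6% at 10 years. No passage supports those durations. Section 1 mentions a departmental paper that "identified 83 patients who had attended a neurology clinic over nine years", which would make longer durations plausible, but the protocol does not say that the pool comes from that series. Recruits are also chosen purposively and are not a random draw from an age band. The number affected therefore cannot be computed; these figures only show how it would vary.

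**What happens after recruitment?** Section 3.4.1 plans a 60-minute interview meant to identify predisposing and precipitating factors. It could hardly do so without establishing when attacks began. Section 5 codes the accounts and builds themes, with no between-group analysis.

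**The case for a change.** The best case for a change is that selection comes before the interview. Knowing age at onset later lets the analyst regroup the ten, but not alter who they are. Section 1 also gives a reason to care about life stage at onset: 45% of the 1973 series had onset in pregnancy or within three years of the start of the menopause, although its authors found no clear hormonal link. Naming the variable would take a sentence and one question before selection. It would also make people with early onset who are now older available to the younger-onset group, which helps in a small pool.

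Part of this stands. The wording is ambiguous, age at first attack fits the primary question better, and a clarifying phrase would do no harm. The claim that the mix is fixed once people are recruited is too strong. Recruitment and data collection both start in January 2018 and collection runs to December, so later participants can be chosen in light of earlier accounts. Purposive sampling seeks variety and does not need exhaustive strata with numeric limits. A firm onset cut-off, with a separate place for onset at 60 or above, could mean turning away willing volunteers.

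**Conclusion.** No change is needed. Section 4 leaves out a detail that the investigators can be expected to fill sensibly; it contains no contradiction and no wrong figure. The supposed contamination needs selection on one age and interpretation on the other, which the protocol does not plan. At the documented minimum of 18 months since onset, the illustrative effect is about 0.2 to 0.4 of five people. It would be larger if the pool has had attacks for many years, which the documents do not establish.

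The conclusion rests on the interview eliciting when attacks began. That is very likely given its stated purpose, but cannot be confirmed because the interview schedule in appendix 1 is not among the text available. It also rests on the age contrast staying exploratory, as Section 4 presents it. On those terms the themes and the answer to the primary question would stand under either reading.
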